Appendix C: List of Tables, Figures, and Listings

The following TLF numbering is completed according to ICH guidelines. The ICH heading number and description are in **bold**. Minor changes from this planned index do not need to be amended in the SAP. Formal organization of tabulations may be changed during programming if appropriate, e.g., tables for the different variables may be combined into a single table, or tables with more than one variable may be split into several tables.

List of tables and figures for analysis

ICH Heading	Table/ Figure Number	Table Description	Analysis Set	Mock reference
14.1		DEMOGRAPHIC DATA		
	14.1.1	Patient number by country	ALL	#DESC
	14.1.2	Patient number by site and country	ALL	#DESC
	14.1.3	Patient disposition	ALL	#DESC
	14.1.4	Trial termination form	SAS	#DESC
	14.1.5	Demographic and baseline characteristics		
	14.1.5.1	Demographics	ALL	#DESC
	14.1.5.2	Medical history		
	14.1.5.2.1	Indication specific medical history (diabetes history)	ALL, SAS	#DESC
	14.1.5.2.2	General medical history/ surgical history including concomitant diseases	ALL, SAS	#AE
	14.1.5.3	History of alcohol or drug abuse	ALL	#DESC
14.2		IMMUNOGENICITY ANALYSES		
	14.2.1	Primary immunogenicity endpoint: Overall ADA incidence		

	14.2.1.1	Overall ADA incidence: Incidence and incidence difference - unstratified	FAS, PPS	#ENDPOINT
	14.2.1.2	Overall ADA incidence: Incidence and incidence difference – by sex	FAS, PPS	#ENDPOINT
	14.2.1.3	Overall ADA incidence: Incidence and incidence difference – by age class	FAS, PPS	#ENDPOINT
	14.2.1.4	Overall ADA incidence: Incidence and incidence difference – by race	FAS, PPS	#ENDPOINT
	14.2.2	Key secondary endpoint: Treatment–induced ADA incidence		
	14.2.2.1	Treatment–induced ADA incidence : Incidence and incidence difference - unstratified	FAS, PPS	#ENDPOINT
	14.2.2.2	Treatment–induced ADA incidence : Incidence and incidence difference – by sex	FAS, PPS	#ENDPOINT
	14.2.2.3	Treatment–induced ADA incidence : Incidence and incidence difference – by age class	FAS, PPS	#ENDPOINT
	14.2.2.4	Treatment–induced ADA incidence : Incidence and incidence difference – by race	FAS, PPS	#ENDPOINT
	14.2.3	Key secondary endpoint: Treatment–boosted ADA incidence		
	14.2.3.1	Treatment–boosted ADA incidence : Incidence and incidence difference - unstratified	FAS, PPS	#ENDPOINT
	14.2.3.2	Treatment–boosted ADA incidence : Incidence and incidence difference – by sex	FAS, PPS	#ENDPOINT

	14.2.3.3	Treatment–boosted ADA incidence : Incidence and incidence difference – by age class	FAS, PPS	#ENDPOINT
	14.2.3.4	Treatment–boosted ADA incidence : Incidence and incidence difference – by race	FAS, PPS	#ENDPOINT
	14.2.4	Analyses of further secondary immunogenicity endpoints		
	14.2.4.1	Incidence and titer of neutralizing activity of ADA-positive patients		
	14.2.4.1.1	Incidence of neutralizing activity of ADA- positive patients		#LONG1 , #LONG2
	14.2.4.1.2	Pre-existing ADA-positive patients: Titer and boosting		#LONG1 , #LONG2
	14.2.4.1.3	Treatment-induced ADA-positive patients: Titer		#LONG1 , #LONG2
	14.2.4.2	Incidence of cross-reactivity of ADA positive patients towards endogenous glucagon		#LONG1 , #LONG2
	14.2.4.3	Kinetics of ADA: The timing and duration of detected ADA response		
	14.2.4.3.1	Kinetics of patients being baseline ADA- negative		
	14.2.4.3.1.1	Figures: Individual display of titers		
	14.2.4.3.2	Kinetics of patients being baseline ADA- positive		
	14.2.4.3.2.1	Figures: Individual display of titers		
14.3		SAFETY ANALYSES		
	14.3.1	Adverse events		

	14.3.1.1	All adverse events - overview	SAS	#AESUM
	14.3.1.2	Adverse events - details		
	14.3.1.2.1	All TEAEs	SAS	#AE
	14.3.1.2.2	All clinical events of interest	SAS	#AE
	14.3.1.2.3	All injections site reactions	SAS	#AE
	14.3.1.2.4	Study-drug-related TEAEs (ADRs)	SAS	#AE
	14.3.1.2.5	TEAEs by causal relationship	SAS	#AE
	14.3.1.2.6	TEAEs by intensity grading	SAS	#AE
	14.3.1.2.7	Serious TEAEs	SAS	#AE
	14.3.1.3	Vital signs related to clinical events of interest	SAS	#DESC
	14.3.1.4	Local tolerability	SAS	#LONG1 , #LONG2
	14.3.2	Routine laboratory		
	14.3.2.1	Hematology		
	14.3.2.1.1	Descriptive statistics: Hematology	SAS	#LAB
	14.3.2.1.2	Change from baseline: Hematology	SAS	#LONG3 / #SHIFT
	14.3.2.2	Clinical chemistry		
	14.3.2.2.1	Descriptive statistics: Clinical chemistry	SAS	#LAB
	14.3.2.2.2	Change from baseline: Clinical chemistry	SAS	#LONG3 / #SHIFT
	14.3.2.3	Coagulation		#LAB
	14.3.2.4	Urinalysis		
	14.3.2.4.1	Descriptive statistics: Urinalysis	SAS	#LAB
	14.3.2.4.2	Change from baseline: Urinalysis	SAS	#LONG3 / #SHIFT
	14.3.2.5	Child bearing potential and results of pregnancy test	SAS	#LONG1 , #LONG2
	14.3.3	Physical examination and vital signs		
	14.3.3.1	Vital signs	SAS	#LONG3

	14.3.3.2	Body measurements	SAS	#DESC
	14.3.3.3	Physical examination		
	14.3.3.3.1	Physical examination: Body systems at screening	SAS	#DESC
	14.3.3.3.2	Physical examination: Changes to previous visits	SAS	#LONG1 , #LONG2
	14.3.4	12-lead ECG		
	14.3.4.1	12-lead ECG: Abnormal findings	SAS	#LONG1 , #LONG2
	14.3.4.2	12-lead ECG: Descriptive statistics for PR interval, QRS interval and QT interval time	SAS	#LONG1 , #LONG2
	14.3.4.3	12-lead ECG: Change from baseline for PR interval, QRS interval and QT interval time	SAS	
	14.3.5	Previous and concomitant medication		
	14.3.5.1	Previous medication	SAS	#CONMED
	14.3.5.2	Concomitant medication	SAS	#CONMED
14.4		PHARMACOKINETIC (PK) AND PHARAMCODYNAMIC (PD) PROPERTIES		#LONG3
	14.4.1	Pharmacokinetics		
	14.4.1.1	Summary statistics of plasma dasiglucagon and GlucaGen concentration table	PKS	#PKCONC
	14.4.1.2	PK metrics	PKS	#PKMETRIC
	14.4.1.3	Figures: Mean analyte concentrations versus time – original scale	PKS	#PK_FDAY
	14.4.1.4	Figures: Individual analyte concentrations versus time curves- original scale	PKS	
	14.4.2	Pharmacodynamics		

	14.4.2.1	Summary statistics of plasma glucose concentration table	PKS	#PKCONC
	14.4.2.2	PD metrics	PKS	#PKMETRIC
	14.4.2.3	Figures: Mean concentrations versus time – original scale	PKS	#PK_FDAY
	14.4.2.4	Figures: Individual concentrations versus time curves- original scale	PKS	
14.5		STUDY DRUG ADMINISTRATION		
	14.5.1	Extent of exposure	SAS	#DESC
	14.5.2	Time between visits and total study duration	SAS	#DESC

List of data listings for analysis

ICH Heading	Listing Number	Listing Description	Comment
16.2		PATIENT DATA LISTINGS	
16.2.1		Discontinued patients	
	16.2.1.1	Trial termination form	
	16.2.1.2	Screening failures	
16.2.2		Protocol deviations	
	16.2.2.1	Protocol deviations	
	16.2.2.2	(Re-check of) Inclusion/ exclusion criteria	
	16.2.2.3	Check of dosing day exclusion criteria	
	16.2.2.4	Randomization	
16.2.3		Patients excluded from the efficacy analysis	
	16.2.3.1	Subject assignment to analysis populations	
16.2.4		Demographic data and baseline characteristics	
	16.2.4.1	Demographics	
	16.2.4.2	Medical history	
	16.2.4.2.1	General medical/ surgical history (incl. concomitant diseases)	
	16.2.4.2.2	Diabetes history	
16.2.5		Compliance and/or drug concentration data	
	16.2.5.1	Informed consent	
	16.2.5.2	Visit dates, number of visits at site, and study duration	
	16.2.5.3	Study drug administration	
	16.2.5.3.1	Assignment of trial medication	
	16.2.5.3.2	Total dose applied, number of days dosed, total duration of exposure	derived data
16.2.6		Primary endpoint, (key) secondary endpoints	
	16.2.6.1	Immunogenicity measurements	
	16.2.6.2	Antibody serum sample for immunogenicity measurements	
	16.2.6.3	Neutralizing antibody measurements (NAb titer)	
	16.2.6.4	Overall ADA incidence, treatment-induced ADA incidence, treatment boosted ADA-incidence	derived data

ICH Heading	Listing Number	Listing Description	Comment
	16.2.6.5	Kinetics: Timing and duration of detected ADA response	derived data
16.2.7		Adverse events and safety endpoints	
	16.2.7.1	Adverse events	
	16.2.7.1.1	Adverse events – CRF entries	
	16.2.7.1.2	Adverse events – MedDRA coding	
	16.2.7.1.3	Study-drug related adverse events (ADRs)	
	16.2.7.1.4	Serious adverse events	
	16.2.7.1.5	Deaths	
	16.2.7.1.6	Vital signs related to clinical events of interest	
	16.2.7.1.7	Injection site reactions	
	16.2.7.2	Local tolerability	
	16.2.7.3	Vital signs including change from baseline	incl. derived data CFB
	16.2.7.4	Body measurements	
	16.2.7.5	Physical examination and changes	
	16.2.7.6	12-lead ECG including change from baseline	
	16.2.7.7	Previous and concomitant medication	
16.2.8		Laboratory	
	16.2.8.1	Hematology including change from baseline	incl. derived data CFB
	16.2.8.2	Biochemistry including change from baseline	incl. derived data CFB
	16.2.8.3	Coagulation	
	16.2.8.4	Urinalysis including change from baseline	incl. derived data CFB
	16.2.8.5	Child bearing potential and pregnancy test	
	16.2.8.6	History of alcohol or drug abuse, alcohol breath test and urine drug screen	
16.2.9		Pharmacokinetics and pharmacodynamics	
	16.2.9.1	Plasma dasiglucagon and GlucaGen measurements	
	16.2.9.2	Individual PK metrics	derived data
	16.2.9.3	Plasma glucose measurements	
	16.2.9.4	Individual PD metrics	derived data
16.2.10		Comments	

Appendix D: Table Layouts

Sponsor
Protocol Number
Table
Title
Analysis Set

	Descriptive Statistics/ Counts (%)		
	dasiglucagon (N=xx)	GlucaGen (N=xx)	Total (N=xx)
Categorical Parameter 1			
Category 1	x (xxx.x)	x (xxx.x)	x (xxx.x)
Category 2	x (xxx.x)	x (xxx.x)	x (xxx.x)
Categorical Parameter 2			
Category 1	x (xxx.x)	x (xxx.x)	x (xxx.x)
Category 2	x (xxx.x)	x (xxx.x)	x (xxx.x)
Category 3	x (xxx.x)	x (xxx.x)	x (xxx.x)
Category 4	x (xxx.x)	x (xxx.x)	x (xxx.x)
Metric Parameter [unit]			
Mean	xx.x	xx.x	xx.x
Median	xx.x	xx.x	xx.x
SD	xx.xx	xx.xx	xx.xx
Min	xx	xx	xx
Max	xx	xx	xx
n	xx	xx	xx

Source: xxx
path\t_program.sas date time

Programmer notes:

Qualitative/ Quantitative variables (Type : DESC)

Rows: Categories/classes of a specific variable

Cells: Qualitative variables: Absolute and relative count within each treatment and class,

Cells: Quantitative variables: Mean, Median, SD (standard deviation), Min, Max, n (valid cases)

Sponsor
Protocol Number
Table
Title
 Analysis Set

		Descriptive Statistics			
		Screening	Treatment period/ Visit	Follow-up	Unscheduled ADA visits
dasiglucagon	Mean	xx.x	xx.x	xx.x	xx.x
	Median	xx.x	xx.x	xx.x	xx.x
	SD	xx.xx	xx.xx	xx.xx	xx.xx
	Min	xx	xx	xx	xx
	Max	xx	xx	xx	xx
	n	xx	xx	xx	xx
Glucagen	Mean	xx.x	xx.x	xx.x	xx.x
	Median	xx.x	xx.x	xx.x	xx.x
	SD	xx.xx	xx.xx	xx.xx	xx.xx
	Min	xx	xx	xx	xx
	Max	xx	xx	xx	xx
	n	xx	xx	xx	xx
Total	Mean	xx.x	xx.x	xx.x	xx.x
	Median	xx.x	xx.x	xx.x	xx.x
	SD	xx.xx	xx.xx	xx.xx	xx.xx
	Min	xx	xx	xx	xx
	Max	xx	xx	xx	xx
	n	xx	xx	xx	xx

Source: xxx
 path\t_program.sas date time

Programmer notes:
 Longitudinal tabulation, horizontal display (Type : LONG1)
 Columns: Time/Visit
 Cells: Quantitative variables: Mean, Median, SD (standard deviation), Min, Max, n (valid cases)

Zealand Pharma A/S
ZP4207-16136 (ZEA-DNK-01711)

Statistical Analysis Plan
19 March 2018

Page 1 of x

Sponsor
Protocol Number
Table
Title
Analysis Set

	Descriptive Statistics/ Counts (%)		
	dasiglucagon (N=xx)	GlucaGen (N=xx)	Total (N=xx)
Screening			
Mean	xx.x	xx.x	xx.x
Median	xx.x	xx.x	xx.x
SD	xx.xx	xx.xx	xx.xx
Min	xx	xx	xx
Max	xx	xx	xx
N	xx	xx	xx
Treatment period/ Visit			
Mean	xx.x	xx.x	xx.x
Median	xx.x	xx.x	xx.x
SD	xx.xx	xx.xx	xx.xx
Min	xx	xx	xx
Max	xx	xx	xx
N	xx	xx	xx
...			

Source: xxx
path\t_program.sas date time

Programmer note:
Longitudinal tabulation, vertical display (Type : LONG2)
Rows: Time/Visit: Screening, further visits, or time T1, T2, etc., Columns: Columns: Treatment group or other
specification, Cells: Quantitative variables: Mean, Median, SD (standard deviation), Min, Max, n (valid cases)

Sponsor
 Protocol Number
 Table
 Title
 Analysis Set

Descriptive Statistics/ Counts (%)

	dasiglucagon (N=xx)	GlucaGen (N=xx)	Total (N=xx)
Screening / Pre-dose			
Mean	xx.x	xx.x	xx.x
Median	xx.x	xx.x	xx.x
SD	xx.xx	xx.xx	xx.xx
Min	xx	xx	xx
Max	xx	xx	xx
n	xx	xx	xx
Visit x / time point X			
Mean	xx.x	xx.x	xx.x
Median	xx.x	xx.x	xx.x
SD	xx.xx	xx.xx	xx.xx
Min	xx	xx	xx
Max	xx	xx	xx
n	xx	xx	xx
Change from screening / pre-dose			
Mean	xx.x	xx.x	xx.x
Median	xx.x	xx.x	xx.x
SD	xx.xx	xx.xx	xx.xx
Min	xx	xx	xx
Max	xx	xx	xx
n	xx	xx	xx
p-value*	x.xxxx	x.xxxx	x.xxxx

Footnote: *.... (only if requested)

Source: xxx

path\t_program.sas date time

Programmer note: Longitudinal tabulation, vertical display (Type: LONG3)

Sponsor
Protocol Number
Table
Title
 Analysis Set

Laboratory panel name = xxxx
 Laboratory test name = xxxx

Visit X/ time point X	Screening/ Pre-dose					
	Negative		Positive		Total	
	N	%	N	%	N	%
dasiglucagon						
Negative	xxx	x.xx	xxx	x.xx	xxx	x.xx
Positive	Xxx	x.xx	Xxx	x.xx	xxx	x.xx
GlucaGen						
Negative	Xxx	x.xx	Xxx	x.xx	xxx	x.xx
Positive	xxx	x.xx	xxx	x.xx	xxx	x.xx
Total	xxx	x.xx	xxx	x.xx	xxx	x.xx

Source: xxx
 path\t_program.sas date time

Programmer notes: Laboratory shift table (Type: SHIFT)

Zealand Pharma A/S
ZP4207-16136 (ZEA-DNK-01711)

Statistical Analysis Plan
19 March 2018

Page 1 of x

Sponsor
Protocol Number
Table
Title
Analysis Set

		Count (%)		Difference in incidences (95% CI of dasiglucagon-GlucaGen)
		dasiglucagon (N=xx)	GlucaGen (N=xx)	
Overall ADA incidence	Yes	xx (xx.x)	xx (xx.x)	
	No	xx (xx.x)	xx (xx.x)	xxx.xx (xx.xx, xx.xx)
	95% CI ¹	(xx.x, xx.x)	(xx.x, xx.x)	

Footnote:

¹: CI for proportion of responder=Yes

Source: xxx

path\t_program.sas date time

Programmer note: Display of incidences and confidence intervals, (Type: ENDPOINT)

Sponsor
Protocol Number
Table
Title
 Analysis Set

	Number of Subjects (%)		
	Event Count		
	dasiglucagon (N=xx)	GlucaGen (N=xx)	Total (N=xx)
Adverse events during screening	xx (xx.x) xx	xx (xx.x) xx	xx (xx.x) xx
Treatment-emergent AEs (TEAEs)	xx (xx.x) xx	xx (xx.x) xx	xx (xx.x) xx
Study drug-related TEAEs (Adverse Drug Reactions (ADRs)) ¹	xx (xx.x) xx	xx (xx.x) xx	xx (xx.x) xx
...	xx (xx.x) xx	xx (xx.x) xx	xx (xx.x) xx

¹ Treatment-related: text to be inserted as defined in AE section of the SAP

Table is based on number of verbatims.

Source: xxx

path\t_program.sas date time

Programmer notes:

Overview of Adverse Events (Type : AESUM)

Sponsor
Protocol Number
Table
Title
 Analysis Set

SOC Preferred Term	Number of Subjects (%) Event Count		
	dasiglucagon (N=xx)	GlucaGen (N=xx)	Total (N=xx)
Any AE	xx (xx.x) xx	xx (xx.x) xx	xx (xx.x) xx
SOC Class 1			
Any PT	xx (xx.x) xx	xx (xx.x) xx	xx (xx.x) xx
PT Term 1	xx (xx.x) xx	xx (xx.x) xx	xx (xx.x) xx
PT Term 2	xx (xx.x) xx	xx (xx.x) xx	xx (xx.x) xx
PT Term 3	xx (xx.x) xx	xx (xx.x) xx	xx (xx.x) xx
PT Term xx	xx (xx.x) xx	xx (xx.x) xx	xx (xx.x) xx
SOC Class 2			
Any PT	xx (xx.x) xx	xx (xx.x) xx	xx (xx.x) xx
PT Term 1	xx (xx.x) xx	xx (xx.x) xx	xx (xx.x) xx
PT Term 2	xx (xx.x) xx	xx (xx.x) xx	xx (xx.x) xx
PT Term 3	xx (xx.x) xx	xx (xx.x) xx	xx (xx.x) xx
PT Term xx	xx (xx.x) xx	xx (xx.x) xx	xx (xx.x) xx
SOC Class xx			
Any PT	xx (xx.x) xx	xx (xx.x) xx	xx (xx.x) xx
PT Term 1	xx (xx.x) xx	xx (xx.x) xx	xx (xx.x) xx
PT Term 2	xx (xx.x) xx	xx (xx.x) xx	xx (xx.x) xx
PT Term 3	xx (xx.x) xx	xx (xx.x) xx	xx (xx.x) xx
PT Term xx	xx (xx.x) xx	xx (xx.x) xx	xx (xx.x) xx

...

A subject with more than one event in a specific category was only counted once
 Percentages based on total no. of subjects in each treatment group
 Table is sorted by descending subject count on the SOC and within each SOC on PT level
 Source: xxx
 path\t_program.sas date time
 Programmer notes: Adverse Event Summary Table (Type : AE)

Sponsor
 Protocol Number
 Table
 Title
 Analysis Set

ATC class Preferred Term	Number of Subjects (%) Event Count		
	dasiglucagon (N=xx)	Glucagen (N=xx)	Total (N=xx)
Number of patients with at least one concomitant medication	xx (xx.x)	xx (xx.x)	xx (xx.x)
ATC1	xx (xx.x) xx	xx (xx.x) xx	xx (xx.x) xx
PT1	xx (xx.x) xx	xx (xx.x) xx	xx (xx.x) xx
PT2	xx (xx.x) xx	xx (xx.x) xx	xx (xx.x) xx
PT3	xx (xx.x) xx	xx (xx.x) xx	xx (xx.x) xx
etc.	xx (xx.x) xx	xx (xx.x) xx	xx (xx.x) xx
ATC2	xx (xx.x) xx	xx (xx.x) xx	xx (xx.x) xx
PT1	xx (xx.x) xx	xx (xx.x) xx	xx (xx.x) xx
PT2	xx (xx.x) xx	xx (xx.x) xx	xx (xx.x) xx
PT3	xx (xx.x) xx	xx (xx.x) xx	xx (xx.x) xx
etc.	xx (xx.x) xx	xx (xx.x) xx	xx (xx.x) xx
...			
ATCX	xx (xx.x) xx	xx (xx.x) xx	xx (xx.x) xx
PT1	xx (xx.x) xx	xx (xx.x) xx	xx (xx.x) xx
PT2	xx (xx.x) xx	xx (xx.x) xx	xx (xx.x) xx
PT3	xx (xx.x) xx	xx (xx.x) xx	xx (xx.x) xx
etc.	xx (xx.x) xx	xx (xx.x) xx	xx (xx.x) xx

Source: xxx
 path\t_program.sas date time
 Programmer note: Concomitant medication tabulation (Type CONMED)

Sponsor
Protocol Number
Table
Title
 Analysis Set

Laboratory panel name = xxxx
 Laboratory test name = xxxx

	N	Mean	Median	SD	SEM	Min	Max	Below	Within	Above	CS	NCS
								reference	reference	reference	N	N
								range	range	range	%	%
dasiglucagon												
Screening	xx	x.xx	x.xx	x.xx	x.xx	x.xx	x.xx	xx xx.xx	xx xx.xx	xx xx.xx	xx xx.xx	xx xx.xx
Visit X	xx	x.xx	x.xx	x.xx	x.xx	x.xx	x.xx	xx xx.xx	xx xx.xx	xx xx.xx	xx xx.xx	xx xx.xx
Visit X	xx	x.xx	x.xx	x.xx	x.xx	x.xx	x.xx	xx xx.xx	xx xx.xx	xx xx.xx	xx xx.xx	xx xx.xx
Visit X	xx	x.xx	x.xx	x.xx	x.xx	x.xx	x.xx	xx xx.xx	xx xx.xx	xx xx.xx	xx xx.xx	xx xx.xx
GlucaGen												
Screening	xx	x.xx	x.xx	x.xx	x.xx	x.xx	x.xx	xx xx.xx	xx xx.xx	xx xx.xx	xx xx.xx	xx xx.xx
Visit X	xx	x.xx	x.xx	x.xx	x.xx	x.xx	x.xx	xx xx.xx	xx xx.xx	xx xx.xx	xx xx.xx	xx xx.xx
Visit X	xx	x.xx	x.xx	x.xx	x.xx	x.xx	x.xx	xx xx.xx	xx xx.xx	xx xx.xx	xx xx.xx	xx xx.xx
Visit X	xx	x.xx	x.xx	x.xx	x.xx	x.xx	x.xx	xx xx.xx	xx xx.xx	xx xx.xx	xx xx.xx	xx xx.xx
Total												
Screening	xx	x.xx	x.xx	x.xx	x.xx	x.xx	x.xx	xx xx.xx	xx xx.xx	xx xx.xx	xx xx.xx	xx xx.xx
Visit X	xx	x.xx	x.xx	x.xx	x.xx	x.xx	x.xx	xx xx.xx	xx xx.xx	xx xx.xx	xx xx.xx	xx xx.xx
Visit X	xx	x.xx	x.xx	x.xx	x.xx	x.xx	x.xx	xx xx.xx	xx xx.xx	xx xx.xx	xx xx.xx	xx xx.xx
Visit X	xx	x.xx	x.xx	x.xx	x.xx	x.xx	x.xx	xx xx.xx	xx xx.xx	xx xx.xx	xx xx.xx	xx xx.xx

Source: xxx
 path\t_program.sas date time

Programmer notes: Laboratory Summary Table (Type: LAB)

Sponsor
 Protocol Number
 Table
 Title
 Analysis Set

Treatment		Descriptive statistics							
		Nominal time after medication administration							
		x	x	x	x	x	x	x
dasiglucagon	n	xx	xx	xx	xx	xx	xx	xx	xx
	Mean	xx.x	xx.x	xx.x	xx.x	xx.x	xx.x	xx.x	xx.x
	Median	xx.x	xx.x	xx.x	xx.x	xx.x	xx.x	xx.x	xx.x
	SD	xx.xx	xx.xx	xx.xx	xx.xx	xx.xx	xx.xx	xx.xx	xx.xx
	Min	xx	xx	xx	xx	xx	xx	xx	xx
	Max	xx	xx	xx	xx	xx	xx	xx	xx
GlucaGen	N	xx	xx	xx	xx	xx	xx	xx	xx
	Mean	xx.x	xx.x	xx.x	xx.x	xx.x	xx.x	xx.x	xx.x
	Median	xx.x	xx.x	xx.x	xx.x	xx.x	xx.x	xx.x	xx.x
	SD	xx.xx	xx.xx	xx.xx	xx.xx	xx.xx	xx.xx	xx.xx	xx.xx
	Min	xx	xx	xx	xx	xx	xx	xx	xx
	Max	xx	xx	xx	xx	xx	xx	xx	xx

Source: xxx
 path\t_program.sas date time

Programmer note :
 PK concentration tabulation (Type PKCONC)

Zealand Pharma A/S
 ZP4207-16136 (ZEA-DNK-01711)

Statistical Analysis Plan
 19 March 2018

[figure not shown]
Page 1 of x

Sponsor
Protocol Number
Table
Title
 Analysis Set

Treatment	Subject	C _{max} (Unit)	t _{max} (Unit)	AUC _{0-30min} (Unit)	AUC _{0-90min} (Unit)
dasiglucagon	xxx	xxx	xxx	xxx	xxx
	xxx	xxx	xxx	xxx	xxx
	...				
	n	x	x	x	x
	Mean	xxx		xxx	xxx
	SD	xxx		xxx	xxx
	Min	xxx		xxx	xxx
	Median	xxx	xxx	xxx	xxx
Max	xxx	xxx	xxx	xxx	
GlucaGen	xxx	xxx	xxx	xxx	xxx
	xxx	xxx	xxx	xxx	xxx
	...				
	n	x	x	x	x
	Mean	xxx	xxx	xxx	xxx
	SD	xxx	xxx	xxx	xxx
	Min	xxx	xxx	xxx	xxx
	Median	xxx	xxx	xxx	xxx
Max	xxx	xxx	xxx	xxx	

Source: xxx
 path\t_program.sas date time
 Programmer note:
 PK metrics tabulation (Type PKMETRIC)
 Table will be adapted to PD metrics.

Figure
Title
Analysis Set

Source: XXX
path\t_program.sas date time
Programmer note: PK metrics figure (Type PK_FDAY)

DATA REVIEW MEETING PROTOCOL

Table of contents

1	LOCATION AND PARTICIPANTS FOR THE BLIND-REVIEW MEETING	2
2	GENERALITIES	3
2.1	MEETING OBJECTIVES	3
3	CRITERIA FOR CLASSIFICATION OF SUBJECTS TO ANALYSIS SUBSETS.....	4
3.1	DEFINITION OF ANALYSIS POPULATIONS.....	4
3.2	CRITERIA LEADING TO AN EXCLUSION FROM A POPULATION INDEPENDENT OF PROTOCOL DEVIATIONS	4
3.3	CRITERIA BASED ON PROTOCOL DEVIATIONS	7
4	SUBJECT DISPOSITION	9
5	SUBJECTS EXCLUDED FROM PP ANALYSIS AND/OR LIST OF SUBJECTS WITH ANY MAJOR PROTOCOL VIOLATION.....	10
6	PROTOCOL DEVIATIONS FOR RANDOMIZED SUBJECTS.....	11
	LIST OF DETECTED PROTOCOL DEVIATIONS	11
7	SIGNATURES.....	12

Version	Date	Changes
V0.1	23-Feb-2018	Initial draft
V1.0	16-Mar-2018	Updated version including PD listings (6) released on 16Mar-2018
V1.1	20-Mar-2018	Updated draft following the BDRM held on 20Mar-2018
V2.0	25-Mar-2018	Final version

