- antiemetic treatment in the form of metoclopramide (Primperan[®]) as per local label, administered before or after dosing

At visit 3:

- patients will be allowed to eat and drink moderately to make them feel comfortable
- a moderate and individualized corrective dose of insulin to convert the induced hyperglycemia to euglycemia, after agreement with the investigator
- antiemetic treatment in the form of metoclopramide (Primperan[®]) as per local label, administered before or after dosing

Patients must be monitored for at least 5 h after dosing at the clinical site for safety observations, including blood glucose monitoring.

Patients will not be discharged until they are considered stable and with a blood glucose level in the range of 70-180 mg/dL. Before discharge, the investigator will provide instructions to the patients on management of their blood glucose levels. Each trial medication will be administered s.c. 3 times in total, with 7 days between dosing (i.e. dosing occurs at Days 0, 7, and 14; Visits 2, 3, and 4). Should the patient experience vomiting following the first or second dasiglucagon or GlucaGen administration, the investigator must ensure normal electrolytes prior to the next dosing day. An electrolyte imbalance can be corrected by administration of an electrolyte supplement or by any other treatment modality considered appropriate by the investigator.

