7.6.4 Safety and tolerability measurements

7.6.4.1 Safety laboratory tests

Routine safety laboratory tests will be performed centrally. Samples for safety laboratory parameters will be collected at Visits 1, 2, 4, 5, and 7. Samples for urinalysis will be collected at Visits 1, 2, 4, and 7. The following parameters will be determined:

- Clinical chemistry: sodium, potassium, calcium, glucose, urea, creatinine, total bilirubin, AST (SGOT), ALT (SGPT), gamma-GT, alkaline phosphatase, total protein, C-reactive protein, HbA_{1c}, C-peptide
- Hematology: hemoglobin, red blood cell count (erythrocytes), hematocrit, platelet count (thrombocytes), total white blood cell count (leucocytes)
- Coagulation: international normalized ratio (INR), fibrinogen (at screening visit only)
- Urinalysis: pH, blood (leukocytes and erythrocytes), protein, glucose, ketones, nitrite

A pregnancy test will be performed at screening (Visit 1) and pre-dose at the three dosing visits (Visit 2, 3 and 4) for women of childbearing potential only.

Alcohol breath tests and urine drug screen (amphetamine, cocaine, MDMA, methamphetamine, opiate/morphine, marijuana) will be performed at Screening (Visit 1) and at Visits 2, 3, and 4.

For further details, please refer to the laboratory manual.

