14.2 Routine laboratory

14.2.1 General

- High (H)/ Low (L) flags will be presented in laboratory listings, where appropriate. If normal ranges are not available, the flagging cannot be performed.
- All data will be listed in the clinical study report as raw data. For the summaries the most recent value will be used in case several measurements have been performed at one visit.

Tabulations will be prepared for each laboratory parameter by treatment group:

1. Laboratory results with continuous variables will be presented with descriptive statistics for each scheduled time point. They will be marked whether they are below (L), within or above (H) the respective reference range. The numbers in each category (above/below/within reference range) will be counted and percentages presented for each laboratory test result, visit and time point.
2. If laboratory values are categorical, the results (e.g. positive/ negative) will be presented with counts and percentages for each visit and time point available.
3. Presentation of 'change from baseline' values: Change from baseline will be evaluated for all laboratory parameters. The change will be calculated by building the difference between the pre-dose value and each post-dose measurement at each visit. Change from baseline values will be presented with descriptive statistics in case of continuous parameters. In case of categorical parameters shift tables will be presented.

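### No planned summary table separates new from pre-existing out-of-range values for the numeric hematology and chemistry tests

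*SAP*

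**What the plan says.** SAP 13.1 lists change from baseline in clinical laboratory parameters as a safety endpoint. SAP 14.2.1 sets out three kinds of display.

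- **Item 1** gives numeric results descriptive statistics, plus counts and percentages below, within and above the reference range for each test, visit and time point.
- **Item 2** covers categorical results: "If laboratory values are categorical, the results (e.g. positive/ negative) will be presented with counts and percentages for each visit and time point available".
- **Item 3** splits change from baseline by type of parameter: "Change from baseline values will be presented with descriptive statistics in case of continuous parameters", and then "In case of categorical parameters shift tables will be presented".

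SAP 14.2.2 and 14.2.3 apply all three items to hematology and clinical chemistry. In Appendix C, the tables "Change from baseline: Hematology" and "Change from baseline: Clinical chemistry" both carry the mock reference LONG3 / SHIFT, as does the urinalysis table. In Appendix D, the shell marked "Programmer notes: Laboratory shift table (Type: SHIFT" crosses Negative/Positive at screening or pre-dose with Negative/Positive at a later time point.

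Protocol 7.6.4.1 lists the tests. The chemistry panel begins "Clinical chemistry: sodium, potassium, calcium, glucose, urea, creatinine, total bilirubin". Protocol 7.5.3 schedules hematology and biochemistry pre-dose and at 30 and 90 minutes at Visits 2 and 4.

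**The concern.** A count of out-of-range values at a post-dose time point mixes two groups: patients who were already out of range before the injection, and patients who moved out of range after it. Only the second group describes a possible treatment effect. A patient who becomes abnormal also cancels in the count against one who returns to normal. A table crossing pre-dose category with post-dose category would keep the groups apart, but the plan provides none for numeric tests.

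Electrolytes make this more than a formality. Amendment 01 added an exclusion for electrolyte values relevant to cardiac conduction. It also added a rule in Protocol 7.4.2 that after vomiting "the investigator must ensure normal electrolytes prior to the next dosing day". A reader of the report will want to know how many patients per arm went from a normal to an abnormal potassium after dosing. As planned, no summary table answers that.

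**Working it through.** The plan states no figure on this point, so there is none to reproduce. The check compares the text with the shells and then bounds what the planned counts can show.

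**1. Which tests are affected.** Protocol 7.6.4.1 lists 5 hematology tests and 15 chemistry tests, 20 in all. Each is reported as a quantity, so under item 3 each gets descriptive change statistics and no shift table. Item 2 gives positive/negative as its example of a categorical result, which matches the SHIFT shell. Of the three panels whose change tables cite SHIFT, only urinalysis can use it as drawn.

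**2. What the remaining outputs show for a numeric test.**

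- LONG3 gives n, mean, median, SD, minimum and maximum of the value and of its change, by arm. It has no range categories.
- LAB gives below/within/above counts and CS/NCS counts, by arm and visit. These are not crossed with the pre-dose category.
- Listings 16.2.8.1 and 16.2.8.2 give values and changes by patient, and 14.2.1 adds H/L flags to the laboratory listings. They give no count by arm.
- The adverse event tables count a laboratory abnormality only if the investigator judged it clinically significant. Protocol 8.1 ties that to a severity needing active management.

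**3. What the LAB counts can identify.** Let N be the patients in an arm with both values, *a* the number low pre-dose and *b* the number low post-dose. The number low at both times lies between max(0, *a* + *b* − N) and min(*a*, *b*). The number newly low is *b* minus that number, so:

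max(0, *b* − *a*) ≤ newly low ≤ min(*b*, N − *a*)

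Inputs: N = 112 / 2 = 56, from the 112 patients expected in SAP section 5 and 1:1 allocation. The values of *a* and *b* are assumed, because the documents give no out-of-range frequencies.

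| *a* pre-dose | *b* post-dose | Lower bound | Upper bound | Newly low, % of 56 |
|---|---|---|---|---|
| 6 | 6 | max(0, 0) = 0 | min(6, 50) = 6 | 0 to 10.7 |
| 5 | 5 | max(0, 0) = 0 | min(5, 51) = 5 | 0 to 8.9 |
| 5 | 8 | max(0, 3) = 3 | min(8, 51) = 8 | 5.4 to 14.3 |
| 0 | 5 | max(0, 5) = 5 | min(5, 56) = 5 | 8.9 exactly |

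In the first row the LAB table shows 10.7% at both time points whether nobody or six patients became newly low. The last row is the kind of edge case where the marginal counts suffice: nobody was abnormal before dosing.

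**The case against.** The strongest reply is that the SAP is coherent as written. LONG3 / SHIFT in Appendix C reads naturally as whichever shell applies, since the same pair is cited for all three panels. The Negative/Positive shell then fits the rule in item 3. This stands. A reader might infer that the shift table is misassigned or that text and shells conflict, but the documents do not require that reading.

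A reader might also infer that new abnormalities are never distinguished anywhere, or that only a mean change is left. Neither is supported. The listings let a reviewer set each flagged value against the patient's pre-dose value. The minimum and maximum in LONG3 would reveal a large fall in one patient even with a mean change of zero. Clinically significant abnormalities needing active management are adverse events. Those starting on or after the first dosing day are tabulated by arm, while conditions found at screening go to medical history or concomitant illness. What these routes lack is a by-arm count of all new out-of-range values.

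The electrolyte exclusion and the rule after vomiting should also reduce the number of relevant pre-dose abnormalities, which narrows the bounds for potassium. They do not exclude every out-of-range value, so the argument weakens the illustration without removing the gap.

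The protocol does not ask for shift tables. Section 10.1.5 of the version following Amendment 01, which Amendment 02 does not list as changed, asks for results to be marked against the reference range and counted. Item 1 delivers that. A randomized reference arm also gives the marginal counts some context. Both points stand, and they are why this is an improvement and not a failure to follow the protocol.

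**Conclusion.** The point holds in limited form. For the 20 numeric hematology and chemistry tests, no planned summary table separates new from pre-existing out-of-range values, and the planned marginal counts generally cannot supply the number.

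The size depends on how many patients are out of range before dosing, which the documents do not state. With none, nothing is lost. With the assumed 6 of 56 at both times, the uncertainty is the full 0 to 6 patients. It may be tempting to add that patients with type 1 diabetes will often be out of range for glucose and HbA1c at baseline. The documents give neither reference ranges nor frequencies, and pre-dose glucose is brought to 70–150 mg/dL, so that is not relied on here. Those two tests are also weak examples: a glucose rise is the intended effect and has its own pharmacodynamic analysis, and HbA1c will not plausibly move within 90 minutes.

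This is a minor reporting improvement. The laboratory analysis is descriptive, no data are lost, and the primary endpoint is unaffected.

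**What to change.** Amend SAP 14.2.1 item 3 so that numeric hematology and chemistry tests also receive a shift table by reference-range category. Add a shell to Appendix D, by arm, with Low/Normal/High pre-dose against Low/Normal/High at each post-dose time point. SAP 13.2 already defines the pre-dose value of the respective dosing visit as baseline. Below each table, give the number and percentage of patients newly out of range post-dose among those in range pre-dose. Keep the Negative/Positive shell for categorical urinalysis results, and point the hematology and chemistry entries in Appendix C to the new shell.

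The cost is a text edit, one shell and more table pages. The reference-range categories are already derived for the LAB tables and the listings, so no new data are needed. The change is best made before database lock, because SAP section 6 treats anything added later as post hoc and exploratory.
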